Effectiveness and Safety of Pharmacopuncture Therapy for Chronic Low Back Pain: Study protocol

Protocol ID : JS-CT-2021-02

Clinical trials : NCT04833309

Document Date : September 30, 2021

Study Design and Setting

This two-armed, parallel, multi-center RCT will competitively recruit 100 patients in the Jaseng Hospital of Korean Medicine, Daejeon Jaseng Hospital of Korean Medicine, Bucheon Jaseng Hospital of Korean Medicine, and Haeundae Jaseng Hospital of Korean Medicine. The study protocol was approved by the Institutional Review Board (IRB) of Jaseng Hospital of Korean Medicine before participant recruitment (JASENG 2021-02-012, JASENG 2021-02-013, JASENG 2021-02-014, JASENG 2021-02-032). Additionally, the study protocol will be registered with Clinicaltrials. gov (NCT04833309) and Clinical Research Information Service (KCT0006088) and continuously updated.

Inclusion/Exclusion Criteria

Inclusion Criteria

- LBP onset \geq 6 months
- Numeric rating scale (NRS) score of LBP \geq 5
- Age 19–70 years
- Signing of the ICF to participate in the clinical trial

Exclusion Criteria

- Diagnosis of a serious disease that may cause LBP (eg, spinal metastasis of tumor, acute fracture, spinal dislocation)
- Progressive neurological defects or severe neurological symptoms
- Pain is caused by soft tissue disease rather than the spine (eg, tumor, fibromyalgia, rheumatic arthritis, gout)
- Other chronic diseases that may hinder the interpretation of treatment effects or outcomes (eg, stroke, myocardial infarction, renal disease, diabetic neuropathy, dementia, epilepsy)
- Current use of steroids, immunosuppressants, antipsychotic agents, or other drugs that may affect study outcomes
- Contraindications for pharmacopuncture, including hemorrhagic diseases, anticoagulant usage, severe diabetes mellitus with risk of infection
- Use of drugs that may affect pain, including non-steroidal anti-inflammatory drugs, or pharmacopuncture therapy within the previous week
- Pregnant or breastfeeding women, as well as women planning to conceive
- Lumbar surgery in the previous three months
- Less than one month since participating in another clinical trial or planning to participate in another clinical trial during the study period or follow-up period within 6 months upon enrolment
- Declining to sign a consent form to participate

- Other disqualifications as determined by the investigators

Interventions

Experimental Group: Pharmacopuncture Therapy

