Pharmacopuncture therapy will be given two times a week for five weeks. With reference to a study on the current trend in pharmacopuncture therapy that used electronic medical records from 12 Korean medical hospitals,¹¹ the treatment will be performed following the physician's clinical judgment. Additionally, all procedure-related matters will be recorded in patients' charts. Pharmacopuncture procedures will be retrospectively reviewed and recorded in a case report form (CRF) for analysis.

Control Group: Physiotherapy

Based on a study on HIRA data, patients with LBP in Korea are treated using a combination of deep heat therapy, superficial heat therapy, transcutaneous electrical nerve stimulation, and intermittent pelvic traction therapy.¹² According to this data, a physician will choose the method, site, and duration of physiotherapy based on their clinical judgment with respect to the patients' symptoms, radiological findings, and improvement levels. Physiotherapy will be performed twice a week for five weeks; further, all matters regarding the physiotherapy, including the type, duration, and site of physiotherapy, will be recorded in patients' charts. The treatment method will be retrospectively reviewed and recorded in CRF for comparison.

Criteria for Discontinuation and Withdrawal

A participant may be discontinued from the clinical trial for the following reasons: Discovery of a previously undetected disease that may affect study outcomes Request for discontinuation during the study period by the participant or their legal representative or withdrawal of consent by the participant Confirmation of pregnancy during the study period Problems regarding the administration of medical and Korean medical procedures for LBP to the participant Other reasons that warrant discontinuation from the study as determined by the researcher

Concomitant Treatment

Pharmacological therapy and medical care for LBP from another healthcare facility may be permitted during the treatment or follow-up period in case of severe pain. The treatment details and frequency will be recorded in the CRF for analysis.

Outcome

Primary Outcome

NRS score of LBP

The LBP intensity within the previous week will be assessed using the NRS. Patients will be instructed to choose a number from 0–10 that best represents their current discomfort level (0 for no pain, 10 for the worst imaginable pain).

Secondary outcomes

NRS score of radiating leg pain

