A pilot study was conducted to compare the effectiveness of pharmacopuncture and physiotherapy in patients with chronic LBP. The between-group difference in the mean reduction of the NRS score for LBP was 1.37 ± 1.94 at the primary endpoint, which is immediately after the 5-week treatment; further, Cohen's d was calculated as 0.71. The correlation between the baseline and endpoint was 0.53. Given a significance of 95% and power of 90%, the sample size was calculated to be 64. Considering a 30% withdrawal rate and the recruitment of participants from four facilities, we aim to recruit 100 patients.

Recruitment

Participants will be recruited using a press release, advertisement posters at the clinical trial facility, and online recruitment sites.

Randomization and Allocation Concealment

A statistician will randomize patients into two groups at the same ratio (50 persons for each) using a randomization table on R studio 1.1.463 (© 2009-2018 R Studio, Inc.). The random sequence will be performed using block randomization; further, the size of each block will be randomly set to 2 or 4. The randomization results will be placed in a sealed opaque envelope and stored in a double-locked cabinet by a third person not involved in the study. The coordinator at each study facility will open the envelope for group allocation. Only participants who provide an ICF will be randomly assigned. The randomization number assigned to each participant will be recorded in the electronic medical record.

Blinding

Since blinding the practitioner administering the treatment and the participants is impossible due to the nature of the intervention, only the outcome assessors will be blinded. Outcome-assessors not involved in the procedure and blinded from the group allocation will perform the assessment before the procedure in an isolated space.

Data Collection and Management

We will use an e-CRF using the Internet-based Clinical Research and Trial management system (iCReaT). The principal investigator will train the outcome assessors and investigators of each facility on the standard operating procedure (SOP) as a reference for the study procedures, including writing a CRF and entering data. A query will be issued for a range check of data values. Data entered into the e-CRF will be cleaned and locked to prevent access by investigators other than the one in charge of data management.

Statistical Methods

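### No stratification by site is specified for four competitively recruiting hospitals and the primary model names no site term; this costs a little precision and causes no bias

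*Combined protocol and SAP*

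**What the plan says.** Study Design and Setting: "This two-armed, parallel, multi-center RCT will competitively recruit 100 patients" at four named hospitals. No quota per hospital is given.

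Randomization and Allocation Concealment: "A statistician will randomize patients into two groups at the same ratio (50 persons for each) using a randomization table". Then: "The random sequence will be performed using block randomization", and "the size of each block will be randomly set to 2 or 4". On use of the envelopes: "The coordinator at each study facility will open the envelope for group allocation". No stratification factor is named. The section does not say whether each hospital has its own list or how envelopes are shared out.

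Interventions: for pharmacopuncture, "the treatment will be performed following the physician's clinical judgment"; for physiotherapy, "a physician will choose the method, site, and duration of physiotherapy based on their clinical judgment" (site here means body site).

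Statistical Methods: the primary linear mixed model has group as the fixed factor, plus covariates selected by a significance criterion at baseline. ANCOVA follows on the imputed data sets. Hospital is named in neither.

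**The concern.** Blocks balance the arms along the list in which they are generated. If that list is shared by four hospitals and used in order of arrival, the total stays close to 1:1 but the split within a hospital is left almost to chance. Hospitals may differ in patients and in practice, and physicians have discretion in both arms, so hospital is a plausible source of outcome variation.

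If the lists are instead kept per hospital, the design is stratified and the analysis should reflect that. The stated covariate rule works against this: read as admitting variables that differ significantly between the arms at baseline, it would leave hospital out precisely because stratification had balanced it.

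On either reading something is unspecified. What is at stake is precision and a defensible, prespecified model.

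**Working it through.** **Inputs from the protocol.** N = 100, 50 per arm, four hospitals, blocks of 2 or 4; difference 1.37, SD 1.94, baseline-endpoint correlation 0.53, power 90%, withdrawal 30%.

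**Assumptions not in the protocol.** Hospital sizes; the share of outcome variance due to hospital, ρ = 0.02 to 0.10; two-sided alpha of 0.05.

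**1. The plan's own figure.** d = 1.37/1.94 = 0.71. A two-sided t-test with 90% power needs 43 per arm. The ANCOVA factor is 1 − 0.53² = 0.7191, and 43 × 0.7191 = 30.9, so 31 per arm, or 62. One more per arm gives the stated 64. Then 64/0.70 = 91.4, so 92, which the protocol raises to 100. The figure is reproduced to within one patient per arm, and nothing below changes it.

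**2. Imbalance within hospitals (simulation with blocks of 2 or 4).**

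One list used in order of arrival, chance that at least one hospital has an arm difference of at least:

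| Assumed hospital sizes | 6 | 8 | 10 |
|---|---|---|---|
| exactly 25 each | 46% | 21% | 7% |
| equally likely, random size | 53% | 27% | 10% |

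Uneven recruitment raises the relative imbalance, mainly in small hospitals. The chance that some hospital is worse than 65:35 is 22% (25 each), 39% (40/30/20/10), 56% (55/25/12/8) and 69% (70/10/10/10).

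Other procedures compatible with the text:
- One list handed out in consecutive runs per hospital: difference at most 4, chance of worse than 65:35 at most 1.5%.
- A separate list per hospital: difference at most 2, chance 0.

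**3. What the imbalance does to the estimate.** Let d_k be the arm difference in hospital k. With one list and 25 per hospital, Var(d_k) ≈ 25 × (1 − 24/99) = 18.9. The hospital-driven part of the treatment estimate has

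SD = √(ρ × 1.94² × 4 × 18.9/50²) = √(ρ × 3.764 × 0.0303).

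- ρ = 0.02: 0.05 NRS points
- ρ = 0.10: 0.11 NRS points

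Over the other assumed hospital sizes the range is 0.04 to 0.11. The planned difference is 1.37, so this is at most 0.11/1.37 = 8% of it.

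**4. Standard error with and without a site term, if lists are by hospital.** Take total SD 1.94, four equal hospitals, 50 per arm and no withdrawals; 1.94 × √(2/50) = 0.388. Without a site term, the residual variance contains the spread of four hospital effects about their own mean: 1.94² × [(1 − ρ) + ρ × 3/4] = 1.94² × (1 − ρ/4). With a site term it is 1.94² × (1 − ρ).

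| ρ | SE without site | SE with site | Ratio |
|---|---|---|---|
| 0.02 | 0.388 × √0.995 = 0.387 | 0.388 × √0.98 = 0.384 | 1.01 |
| 0.10 | 0.388 × √0.975 = 0.383 | 0.388 × √0.90 = 0.368 | 1.04 |

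The reported standard error would be about 1% to 4% too wide. Withdrawals change both columns alike and leave the ratio as it is.

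**5. Price of adjusting if one common list was used.** With chance imbalance present, a site-adjusted comparison keeps about 97% of the information on average and 92% at the 5th percentile. If hospitals do not differ at all, the average cost is 1/√0.97 = 1.015, a standard error about 1.5% larger.

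**The case against.** **The documents do not say there is one common list.** A reader might infer it from the single table and the fixed 50 per arm, and conclude that hospitals will be badly unbalanced. The text is silent. Lists per hospital, or runs of one list sent to each hospital, fit it too, and both keep hospitals nearly balanced. This objection stands: the percentages in step 2 are conditional on order-of-arrival use and on assumed hospital sizes.

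**Imbalance between hospitals is not confounding.** A reader might infer that hospital differences are mixed into the treatment effect as bias. With concealed random allocation the imbalance arises by chance and averages to zero. The SD of 0.05 to 0.11 is part of the total variance from which the usual standard error is computed; it is not an extra error on top of it. This stands in full.

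**The other branch is conservative.** Omitting site after stratifying widens the interval. It costs a little power and does not raise the false-positive rate. This stands.

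**Physician discretion is a weak argument for a site term.** It chiefly produces treatment effects that vary by hospital or practitioner, which neither stratification nor a site main effect removes. This largely stands; discretion only makes some hospital-level variation more plausible.

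**Lists per hospital are not free.** The trial is open-label at the point of treatment, and the coordinator at each hospital opens the envelopes. With blocks of 2 or 4 on a local list, the next allocation can often be guessed. This stands and shapes the fix.

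None of these explains why hospital is missing from both the randomisation description and the model.

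**Conclusion.** The point holds as a low-priority but concrete improvement. The plan specifies no stratification by site, leaves open how envelopes are divided, and names no site term in the primary mixed model or the ANCOVA. Under a common list used in order of arrival, an arm difference of 6 or more in at least one hospital is about as likely as not (46% to 53%, depending on assumed hospital sizes). Under lists per hospital, the standard error is overstated by about 1% to 4% for an assumed site variance share of 0.02 to 0.10.

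Overall 1:1 balance is protected either way, the sample size is unaffected, and the treatment comparison is not biased. The documents do not support a stronger claim of demonstrated imbalance or confounding by hospital. Hospital sizes and the variance share are assumptions; the protocol gives neither.

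**What to change.** 1. Include site as a prespecified fixed factor in the primary mixed model and the ANCOVA, whatever the baseline significance tests show.
2. Generate a separate list for each of the four hospitals and state that envelopes are prepared and numbered per hospital.
3. Use random block sizes larger than 2 and 4, for example 4 and 6, and keep them from the hospitals: record them in a restricted document held by the statistician instead of the protocol.
4. Describe 50 per arm as a target.

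Cost: four lists instead of one, and 3 degrees of freedom. If hospitals do not differ, there is a slight loss of precision. Unfinished blocks mean totals may miss 50:50 by a few patients. With blocks of 4 and 6, the arm difference is at most 3 within a hospital (half the largest block), so 4 × 3 = 12 overall in the extreme case, or 56:44. With blocks of 2 and 4 the corresponding limits are 2 and 4 × 2 = 8, or 54:46, but the next allocation is easier to guess.

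If allocation has already begun, item 1 can still be adopted before the data are analysed, and the way envelopes were actually divided should be reported.

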The EQ-5D-5L is the most widely used indirect evaluation tool for the health state. The descriptive system comprises five dimensions: mobility, self-care, usual activities, pain/discomfort, and anxiety/depression. Each dimension has 5 levels: no problems, slight problems, moderate problems, severe problems, and extreme problems. The patient is asked to indicate their health state by ticking the box next to the most appropriate statement in each of the five dimensions. This decision results in a 1-digit number that expresses the level selected for that dimension. The digits for the five dimensions can be combined into a 5-digit number that describes the patient's health state. There are specific weights for the level of each category; moreover, these weights and constant numbers are used to compute the preference score. We

will use the questionnaire of the Korean-adapted version, which has been shown to be reliable and valid.

Credibility and Expectancy

Participants' expectations for the treatment will be assessed using a 9-point Likert scale. At the enrolment visit, the participants will respond to the question, "How much pain relief do you expect from the pharmacopuncture therapy and physiotherapy? (1 = not at all, 5 = somewhat, and 9 = very much)

Cost Analysis

Cost analysis will be performed using a structured questionnaire for official/unofficial medical costs, nonmedical expenses, time costs, and cost of productivity loss. The official medical cost refers to the cost spent utilizing healthcare facility services, while the unofficial medical cost refers to the cost spent on purchasing health supplements and medical equipment. Non-medical expenses refer to the cost incurred while utilizing healthcare, including transportation, patient's time, and caregiver cost. Cost of productivity loss refers to the cost incurred by lost productivity due to absenteeism and presenteeism due to the disease. The work productivity and activity impairment questionnaire will be used to determine productivity loss; additionally, this will be converted to cost for cost-effectiveness analysis.

Drug Consumption

The types and doses of drugs (rescue drugs) taken for LBP during the study period will be surveyed and recorded at each visit. The frequency of other treatment types, including physiotherapy and injections, will be recorded.

Adverse Events

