We will perform both intention-to-treat (ITT) and per-protocol (PP) analyses, with ITT as the primary analysis. For the PP analysis, we will include participants who complete at least seven treatment sessions over 5 weeks. Missing data will be handled by multiple imputation (MI) for analysis of covariance (ANCOVA) and comparison of area under the curve (AUC), as well as

the mixed model for repeated measures for the linear mixed model. For survival analysis, outcomes after the missing time point will be censored. For sensitivity analysis, the last observation carried forward (LOCF) will be used for missing data imputation; further, the normality of distribution will be tested. Nonparametric data will be analyzed using the Wilcoxon-rank sum test. Sociodemographic characteristics and treatment expectancy of the participants will be assessed according to the group. Continuous variables will be presented as mean (SD) or median (quartile), with between-group differences being analyzed using Student's t-test or Wilcoxon-rank sum test, depending on their distribution. Categorical variables will be presented as frequency (%) and analyzed with the chi-square test or Fisher's exact test.

The study endpoints are the differences in the extent of changes in continuous outcomes (NRS, VAS, NDI, NPQ, EQ- 5D-5L, SF-12) at each time point from the baseline. As the primary analysis, we will use a linear mixed model with the covariant factors significantly different from the baseline as covariates and the group as the fixed factor. Next, ANCOVA will be performed on sets processed by MI and LOCF.

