To compare the total difference in each outcome within a certain period (treatment period and total study period), the AUC will be calculated for each time point after randomization and compared using Student's t-test. Further, the proportion of patients whose NRS and VAS scores dropped by > 50% from the baseline values will be compared at each time point. The time from randomization to lumbar recovery, which was defined as > 50% reduction in the pain indices, will be compared using Kaplan-Meier survival analysis. Further, the curves will be compared using the Log rank test. Additionally, hazard ratios will be compared using the Cox proportional hazard model. The significance level will be set at 0.05 for all analyses. All statistical analyses will be performed using the SAS 9.4 (© SAS Institute, Inc., Cary, NC, USA) or R studio 1.1.463 (© 2009-2018 RStudio, Inc.) software. Statistical significance will be set at $p < 0.05$.

In case the superiority test fails, a non-inferiority test will be performed. The non-inferiority margin will be set to -1 (NRS), which represents half of the minimal clinically important difference. Pharmacopuncture will be considered non-inferior to physiotherapy if the lower bound of the 95% confidence interval (CI) of the between-group difference of the NRS score reduction does not exceed the non-inferiority margin.

Data Monitoring

The monitoring staff will supervise the clinical trial process, as well as periodically review and confirm whether the study is performed and recorded according to the protocol, SOP, clinical trial management standards, and applicable regulations. The clinical trial will be monitored by the monitoring staff of each clinical trial facility and the sponsor institution using periodic visits and phone calls. At the monitoring visits, the monitoring staff will check the original participant records and data storage (study files). Further, they will inspect the clinical trial procedure and discuss any problems with the investigators.

In case of unexpected or unacceptable risks to participants or occurrence of serious adverse events related to pharmacopuncture or physiotherapy in $\geq 25\%$ of the participants, the clinical trial may be paused. The analysis will be only accessed by the statistician and principal investigator; additionally, the final decision to terminate the study will be made by the principal

investigator

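### The fallback non-inferiority claim names no analysis set and so rests on ITT alone, and no prespecified NRS analysis accounts for permitted outside back-pain care

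*Combined protocol and SAP*

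**What the plan says.** All references are to the combined protocol and SAP.

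- **Analysis sets (Statistical Methods).** "We will perform both intention-to-treat (ITT) and per-protocol (PP) analyses, with ITT as the primary analysis". The PP criterion is: "For the PP analysis, we will include participants who complete at least seven treatment sessions over 5 weeks". No other condition is attached, and the sentence does not say that the sessions must be of the assigned treatment.
- **Planned sessions (Interventions).** "Pharmacopuncture therapy will be given two times a week for five weeks" and "Physiotherapy will be performed twice a week for five weeks", so ten sessions in each arm.
- **Outside care (Concomitant Treatment).** The permission reads: "Pharmacological therapy and medical care for LBP from another healthcare facility may be permitted during the treatment or follow-up period in case of severe pain". Then: "The treatment details and frequency will be recorded in the CRF for analysis".
- **Recording (Outcome, Drug Consumption).** Rescue drugs are surveyed at each visit. In addition, "The frequency of other treatment types, including physiotherapy and injections, will be recorded". Physiotherapy is the control treatment.
- **Fallback claim (Statistical Methods).** "In case the superiority test fails, a non-inferiority test will be performed". A margin of -1 NRS and a confidence-interval rule follow, but no analysis set is given. I read the rule as requiring the lower 95% limit to lie above -1.

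**The concern.** Care that moves the two arms together has opposite consequences for the two tests. For superiority it costs power. For non-inferiority it makes a false claim easier, because a pharmacopuncture patient who is doing badly may improve through physiotherapy, injections or drugs obtained elsewhere, and that improvement then counts towards non-inferiority.

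Outside care here is tied to severe pain. If pharmacopuncture really is worse, which is the case a non-inferiority test must guard against, that arm would be expected to seek more of it. Participants are not blinded (Blinding), so care-seeking may also differ by arm for that reason.

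The sponsor already treats such care as able to distort pain scores: recent use of pain-affecting drugs or pharmacopuncture, within one week, is an exclusion criterion at entry. The primary NRS also has a one-week recall, but the analysis has no corresponding provision at the endpoint.

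As written, the fallback claim needs no support from a second analysis set, and no NRS analysis shows how far it depends on outside care.

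**Working it through.** **Inputs.** From Sample Size Calculation: SD 1.94, pilot difference 1.37, baseline-endpoint correlation 0.53, 30% withdrawal, 100 patients. From Randomization: 50 per arm. From Statistical Methods: margin -1 and a 95% interval, taken as two-sided, so 2.5% one-sided.

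**1. Reproduce the planned sample size.** Baseline-adjusted SD = 1.94 × √(1 − 0.53²) = 1.645. With a difference of 1.37, two-sided 5% and 90% power, the normal formula gives 31 per arm. The noncentral-t version gives 32 per arm (power 0.906; 0.897 at 31), which is the stated total of 64. The planned number is not in dispute, and the adjusted SD is evidently the sponsor's own working figure.

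**2. Standard error of the difference.** Evaluable per arm = 50 × 0.70 = 35. SE = 1.645 × √(2/35) = 0.393. Without baseline adjustment, SE = 1.94 × √(2/35) = 0.464.

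**3. False non-inferiority at the margin.** Let the true difference be -1. Let outside care shift the observed difference towards zero by a net amount s, meaning the mean gain in the pharmacopuncture arm minus the mean gain in the control arm. Then P(lower limit > -1) = Φ(s/SE − 1.96).

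| Net shift s | 35 per arm, SD 1.645 | 35 per arm, SD 1.94 | 50 per arm, SD 1.645 |
|---|---|---|---|
| 0 | 2.5% | 2.5% | 2.5% |
| 0.1 | 4.4% | 4.1% | 4.9% |
| 0.2 | 7.3% | 6.3% | 8.8% |
| 0.3 | 11.6% | 9.5% | 14.7% |

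For example, with s = 0.3: 0.3/0.393 − 1.96 = −1.197, and Φ(−1.197) = 11.6%.

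**4. What such a shift would take.** If other-arm treatment simply brought a pharmacopuncture patient up to the comparator mean, the gain at the margin would be 1 point. A net shift of 0.2 or 0.3 then needs 20% or 30% of that arm to receive it, with no gain from outside care among controls. Equal mean gains in both arms give s = 0 and no bias.

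**5. Effect on reaching the fallback.** Suppose the pilot difference is diluted by 10%, 20% or 30%. Superiority power at 35 per arm (adjusted SD) is Φ(1.37 × (1 − c)/0.393 − 1.96), which falls from 0.94 to 0.88, 0.80 and 0.68. The same dilution therefore makes use of the fallback more likely.

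**6. What the planned analyses cover.** The MI, mixed-model and LOCF provisions all deal with missing data. None concerns an NRS score that was observed after outside care.

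**The case against.** Permitted rescue care is not a protocol deviation, so a PP set that retains its users is consistent with the plan. Treatment in both arms follows physician judgement and ITT is primary, which fits a comparison of treatment policies with outside care included. This stands. A reader might infer that the PP set is wrongly defined and that everyone with outside care should be removed. The protocol does not support that.

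Exclusion could also do harm. Users of outside care are likely to be poor responders, so removing them can flatter pharmacopuncture. As an illustration, assume 20% of that arm is removed and the correlation between use and poor outcome is 0.5. The mean of the remaining 80% rises by about 0.5 × SD × 0.35, which is 0.29 (SD 1.645) to 0.34 (SD 1.94). That is as large as the 0.3 contamination shift above. This stands too.

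Three further points limit the concern:

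- Outside care is open to both arms, so a gain in the pharmacopuncture arm alone cannot be read as bias; only the net difference matters.
- Drug consumption is listed among the outcomes, so differential use may well be tabulated. It would be too strong to say the data go unused. The gap is that no NRS analysis uses them.
- Recording the frequency of physiotherapy is data capture and does not show that cross-over is expected. Whether the permission covers pharmacopuncture elsewhere for controls is unclear, because it refers to medical care while the discontinuation criteria distinguish medical from Korean medical procedures.

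None of this supplies an analysis set for the non-inferiority test or a prespecified way to examine its dependence on outside care.

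**Conclusion.** The concern holds in a limited form. The fallback non-inferiority claim has no named analysis set and so rests on ITT alone. Outside care is recorded, but no planned NRS analysis uses it, and the session-count PP set does not separate out patients who had the other arm's treatment. If outside care narrows the arm difference, the claim is anti-conservative: about 7% or 12% false claims instead of 2.5% for net shifts of 0.2 or 0.3 points (6% or 9% with the unadjusted SD).

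These figures assume 35 evaluable patients per arm, a true difference exactly at the margin, and shifts for which the protocol gives no basis in frequency. A reader might take 7% to 12% as this trial's actual error rate; it is not. Nor does the point undermine a positive superiority result, because dilution of this kind works against superiority.

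**What to change.** 1. **Decision rule.** State that non-inferiority is claimed only if the lower 95% confidence limit lies above -1 in both the ITT and the PP set, and define PP as at least seven sessions of the assigned treatment. This cannot make the claim easier. It guards mainly against dilution from poor attendance; outside care needs item 2.
2. **Supplementary analysis.** Prespecify a second run of the same non-inferiority comparison that uses the recorded outside-care data under one rule applied identically in both arms, and report it beside ITT. For example, set the week-5 NRS change to zero for any patient who received the other arm's treatment between randomisation and the primary assessment, or rescue drugs or injections for back pain within its one-week recall window. Show use by arm next to it. If a share p of each arm is set to zero and use is unrelated to response, the difference shrinks by a factor (1 − p). The result is therefore informative mainly when use differs between arms, and it should be supplementary, not a third condition for the claim.
3. **Exclusion.** Removing users of outside care from PP should be at most an additional sensitivity analysis, for the selection reason given above.

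The permission for rescue care is unchanged. The rule must be fixed before results are seen, since a set chosen after superiority has failed would carry little weight.

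**Cost.** SAP wording and one extra analysis on data already collected. Non-inferiority becomes somewhat harder to claim. With a true difference of zero and the adjusted SD, the chance of meeting the rule in a single set is Φ(1/SE − 1.96): 0.72 at 35 per arm (SE 0.393) and 0.68 at 32 per arm (SE 0.411), so a somewhat smaller PP set costs a few percentage points, and requiring both sets can only lower the chance further.
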